3.1. Rationale for Selection of Primary and Key Secondary Endpoints

The primary and secondary endpoints were selected based on the clinical relevance and potential import for guiding the treatment of pexidartinib in patients with TGCT. Information on objective (tumor response), subjective (PROMIS-Physical Function Questionnaire, European Quality of Life Five Dimension Five Level Scale [EQ-5D-5L]), and safety measures for subjects with TGCT are all relevant for prescribers, patients, and regulators.

4. STUDY DESIGN

4.1. Overall Design

This is a Phase 4, multicenter study in subjects with TGCT (pigmented villonodular synovitis [PVNS] or giant cell tumor of the tendon sheath [GCT-TS]) who were previously treated with pexidartinib in one of the following studies (hereafter referred to as prior study): (PLX108-10 (ENLIVEN), PLX108-01, PL3397-A-A103, and PL3397-A U126). Based on these prior studies, subjects will be enrolled from investigational sites in the US, European Union (EU) (Netherlands, Spain, Hungary, and Italy), Australia, and Taiwan. The subject population is described in Section 5.

The study start date is the date when the first subject has signed an informed consent and the study end date will be the completion of the last patient's Follow-up Visit. A subject is eligible to be enrolled into the study when the Investigator or designee has determined the subject is currently receiving pexidartinib treatment as part of one of the prior studies and meets the inclusion/exclusion criteria for this study (Section 5).

4.1.1. Design Overview

Subjects in the 4 ongoing TGCT studies will be screened at the "End-of-Treatment (EOT) visit" (i.e., the visit at which they receive their final dose of pexidartinib) of their previous study, at which time they can elect to enroll in the PL3397-A-U4003 study in 1 of 2 cohorts – the **Treatment Continuation Cohort** (where their existing pexidartinib treatment will continue uninterrupted) or **Treatment-Free/ Re-Treatment Cohort** (where they will discontinue pexidartinib treatment with the possibility to re-initiate treatment over the course of the study). Subjects who elect to not enroll in the PL3397-A-U4003 study will remain in their current study and complete their respective End-of-Study activities.

Subjects who elect to enroll in PL3397-A-U4003 will sign an institutional review board (IRB)/independent ethics committee (IEC)-approved informed consent form (ICF). By signing the ICF, subjects will permit acquisition and data transfer of any data collected in their precursor study, including, but not limited to, medical and surgical history, and prior medications. The assessments performed during the preceding study's End-of-Treatment visit will serve as the Baseline measurements for the PL3397-A-U4003 study.

Eligible subject who choose to continue pexidartinib treatment in the **Treatment Continuation Cohort** will remain on their current dosage regimen of pexidartinib and undergo clinical assessments at 3-month intervals for the duration of the study.

Subjects who choose to discontinue pexidartinib will be enrolled in the Treatment-Free period of the **Treatment-Free/Re-Treatment Cohort**. These subjects will stop pexidartinib dosing at entry into PL3397-A-U4003 (i.e., after their final dose at the preceding study's EOT visit). Subjects will undergo clinical assessments 1 month after enrollment, 3 months after enrollment, and then at 3-month intervals. Subjects will remain treatment-free until retreated with pexidartinib, based on the Investigator and/or subject's discretion. Considerations are given to tumor response, subjective and/or functional measures, and safety parameters in the decision-making process. The rationale for discontinuation and re-treatment with pexidartinib will be recorded accordingly.

For subjects who restart pexidartinib treatment in the Re-Treatment period of the **Treatment-Free/Re-Treatment Cohort**, pexidartinib will be administered at the dosage level at which the subject completed the prior study. Doses must be administered on an empty stomach (at least 1 hour before or 2 hours after a meal or snack), at approximately the same times of the day, and approximately 12 hours apart. The full set of study assessments will be performed (Baseline-2). During re-treatment, Investigators will ensure weekly liver monitoring tests for the first 8 weeks, then every 2 weeks for the next month, then every 3 months or more frequently as directed by the Investigator (see [Table 6.3](#)).

The Investigator will evaluate the quarterly magnetic resonance imaging (MRI) scans to perform a qualitative tumor assessment (i.e., stable disease) for subjects in the **Treatment-Free/Re-Treatment Cohort**. Additional assessments may be conducted based on worsening of tumor response as deemed necessary by the Investigator. For those subjects who restart pexidartinib treatment in the Re-Treatment period of the **Treatment-Free/Re-Treatment Cohort**, the response should note “Progression” and the assessments after re-treatment should use Baseline 2 as the reference to determine Progression or Non-Progression.

The PROs (PROMIS PF and EQ-5D-5L) will be performed every 3 months for all subjects.

Ongoing safety will include serum chemistry, hematology, urinalysis, coagulation, ECG, hormone testing, and physical examination, and subjects will be monitored for adverse events (AEs)/TEAEs.

Subjects on treatment who end their study participation early with no radiologic disease progression will undergo a final MRI 3 months \pm 14 days after their last dose of study treatment or before any new TGCT therapy, including surgery.

Subjects who discontinue early from the study will complete the End-of-Study (EOS)/EOT visit and will be withdrawn from the study.

The subject population is described in [Section 5](#). A flow diagram of the study is presented in [Figure 1.1](#).

4.1.2. End of Study

The primary completion date is the date when the last of those subject(s) entering the Treatment-Free period of the **Treatment-Free/Re-Treatment Cohort** either progresses to and completes the Re-Treatment period and/or remains treatment-free for the duration of the study. This date is used as the cut-off date for the analysis of the primary efficacy endpoint(s) of the study.

The overall end of the study will occur when the last subject has their last visit/contact.

The subject’s EOS is the date of their last study visit/contact.

4.1.3. Dose Regimen

Pexidartinib will be provided as an oral, daily administration at the dosage level at the end of their prior study. Doses will be taken on an empty stomach (at least 1 hour before or 2 hours after a meal or snack), at approximately the same times of the day, and approximately 12-hours apart.

Note: Dose escalation of pexidartinib treatment is not permitted during the course of this study.

4.1.4. Duration

The study start date is the date when the first subject signs the ICF and the study continues until the last subject has had their last visit.

Duration of Treatment and Subject Participation

Subjects will be evaluated for eligibility at the last visit of their prior study.

Subject in the **Treatment Continuation Cohort** will undergo study assessments at 3-month intervals for a maximum of 24 months.

Subjects in the **Treatment-Free period of the Treatment-Free/Re-Treatment Cohort** will undergo study assessments at 1 month after enrollment, 3 months after enrollment, and then at 3-month intervals until either re-treatment with pexidartinib or for a maximum of 24 months.

Subjects in the **Re-Treatment period of the Treatment-Free/Re-Treatment Cohort** will undergo study assessments at M1, M2 and then at 3-month intervals. The maximum duration for any subject within the combined periods of the **Treatment-Free/Re-Treatment Cohort** is 24 months. Liver safety assessments will follow a separate schedule (See [Table 1.3](#)).

The study will end with the last subject's last visit. A post-trial access plan, delineating options for access to pexidartinib, will be available for subjects after completing their study participation if the subject is benefiting from the study drug.

Overall Study Duration

Anticipated total duration of the study is expected to be approximately 24 months. See Section [4.1](#) for the definition of study start and Section [4.1.2](#) for the definition of the overall EOS.

Study Drug Continuation After the End of Study

A post-trial access plan, delineating options for access to pexidartinib, will be available for subjects after completing their study participation if the subject is benefiting from the study drug.

4.2. Rationale for Study Design

This Phase 4 study design assumes that in subjects with TGCT, having stable disease and who are being treated with pexidartinib, it is possible to suspend treatment until there are signs of disease progression. It is assumed that re-initiation of treatment with pexidartinib will again lead to stabilization of the subject's disease and potentially to a diminution of the disease.

4.3. Justification for Dose

The dose used during the subject's prior study was found to be safe and effective for the subject.

5. STUDY POPULATION

5.1. Inclusion Criteria

Subjects must meet all of the following criteria to be eligible for enrollment into the study:

1. Currently enrolled and have not been discontinued from pexidartinib treatment in one of the following studies: Study PLX108-10 (ENLIVEN), Study PLX108-01, Study PL3397-A-A103, or Study PL3397-A-U126.
2. Willing and able to complete the PROMIS (Physical Function Scale) and EQ-5D-5L (European Quality of Life) throughout the study.
3. Willing and able to provide written informed consent form (ICF) prior to any study-related procedures and to comply with all study requirements.
4. Females of reproductive potential must have a negative urine pregnancy test at Screening/Baseline (to be confirmed by a serum pregnancy test taken on the End-of-Treatment visit of their prior study) and should be advised to use an effective, non-hormonal method of contraception during treatment with pexidartinib and for 1 month after the last dose. Males with female partners of reproductive potential should be advised to use an effective method of contraception during treatment with pexidartinib and for 1 month after the last dose. Female partners of male patients should concurrently use effective contraceptive methods (hormonal or non-hormonal).

Note: A female is considered of reproductive potential following menarche and until becoming postmenopausal (no menstrual period for a minimum of 12 months) unless permanently sterile (undergone a hysterectomy, bilateral salpingectomy or bilateral oophorectomy) with a confirmed by follicle stimulating hormone (FSH) test level >40 mIU/mL.

5. Male subjects must not freeze or donate sperm starting at Screening and throughout the study period, and for at least 5 half-lives or 1 month after the final study drug administration, whichever is longer.

Female subjects must not donate, or retrieve for their own use, ova from the time of Screening and throughout the study treatment period, and for at least 1 month or 5 half-lives after the final study drug administration, whichever is longer.

5.2. Exclusion Criteria

Subjects who meet any of the following criteria are NOT eligible for enrollment into the study

1. Subject has a clinically significant abnormality identified by the Investigator at Screening on physical examination, laboratory tests, or electrocardiogram which, in the judgement of the Investigator, would preclude the subject's safe completion of the study.
2. Exposure to another investigational drug or current participation in other therapeutic investigational procedures, besides pexidartinib studies, within 1 month prior to start of study treatment. Any known contraindication to treatment with, including hypersensitivity to, the study drug(s) or excipients in pexidartinib.

5.3. Screening Failures, Rescreening, and Subject Replacement

If a subject does not meet eligibility criteria at Screening, they may be rescreened based on the Investigator's discretion. Details will be included in the *PL3397-A-U4003 Study Manual*.

6. STUDY TREATMENT(S)

See [Figure 1.1](#) for treatment sequence.

6.1. Study Drug(s) Description

[Table 6.1](#) describes the formulation, dose, regimen, duration, packaging, and labeling of pexidartinib.

Table 6.1: Study Drug Dosing Information

Study Drug Name	Pexidartinib
Dosage Formulation	200 mg capsules
Dosage Level(s)	The dose level at end of prior study will serve as the starting dose level. Note: Dose escalation of pexidartinib treatment is not permitted during the course of this study.
Route of Administration	Oral
Dosing	Pexidartinib should be administered twice daily approximately 12 h apart on an empty stomach (at least 1 hour before or 2 hours after a meal or snack).
Duration	Daily until subject's end of study
Packaging	PLX3397-HCl 200 mg capsules are manufactured, packaged, and labeled according to Good Manufacturing Practices and Good Clinical Practices (GCP). Packaging will clearly display the name of product, storage condition, and other required information as applicable in accordance with local regulations.
Labeling	Packaging will be labeled as required per local regulatory requirement.

6.2. Preparation, Handling, Storage, and Accountability for Study Drug(s)

6.2.1. Preparation, Handling, and Disposal

All pexidartinib is supplied as 200-mg capsules that need no further preparation at the study sites.

Procedures for proper handling and disposal should be followed in compliance with the Standard Operating Procedures (SOPs) of the Investigational site.

6.2.2. Administration

Pexidartinib is provided as 200-mg capsules for oral, daily administration. Subjects are to be administered the dosage level at which they completed their prior study. Doses must be administered on an empty stomach (at least 1 hour before or 2 hours after a meal or snack), at approximately the same times of the day, and approximately 12 hours apart. Administration with food (particularly with high proportion of fat) may result in increased exposure to pexidartinib and should be avoided. Dose reductions and interruptions are permitted according to pre-specified guidelines.

On the day of the scheduled visit, subjects will be instructed to take their morning and evening dose at the usual time of study treatment. Subjects should be told to bring their bottle containing all unused study treatment to the clinic for accountability.

Between clinic visits, subjects will administer their study treatment at home and record the dosing information in the study dosing Diary. Missed doses (those generally outside of a \pm 2-hour dosing window) should be skipped and **NOT** administered as a double dose at the next dosing time point. Subjects who vomit their dose should be instructed **NOT** to make up that dose. Study sites will call subjects on a weekly basis as reminders to bring IP bottles to site visits and to complete their diaries. During these calls, study sites may also collect other information, including AEs and concomitant medications.

Further details on study treatment administration are contained in the *PLX3397-A-U4003 Pharmacy Manual*.

6.2.3. Storage

Pexidartinib should be stored at the sites in a secure, controlled facility and only provided to subjects who signed an ICF and are participating in the study. Pexidartinib 200 mg capsules should be stored at controlled room temperature (should not be stored above 25°C/77°F). Excursions are permitted to 15°C to 30°C (59°F to 86°F). If storage conditions are not maintained per specified requirements, then the Sponsor or contract research organization (CRO) should be contacted. Subjects will be instructed to store pexidartinib at room temperature out of the reach of children or other cohabitants.

6.2.4. Drug Accountability

When a drug shipment is received, the Investigator or designee will check the amount and condition of the drug against the shipping documentation.

Documentation of receipt of shipment should be returned as instructed on the form. The original will be retained at the study site.

In addition, the Investigator or designee shall contact the Sponsor or designee as soon as possible if there is a problem with the shipment.

The Investigator is responsible for study drug accountability, reconciliation, and record maintenance (i.e., documentation of receipt of shipment, dispensation/return record, and certificate of destruction/return receipt).

Additional information can be found in the *PL3397-A-U4003 Study Manual*.

6.3. Measure to Minimize Bias: Randomization and Blinding

Not applicable.

6.4. Treatment Compliance

Dosing compliance for pexidartinib will be assessed by means of capsule counts remaining or bottles returned. All pexidartinib packaging will be returned at each subject visit; an accounting of capsules will be made and recorded in the electronic case report form (eCRF). If zero capsules were returned, subjects are asked whether any were disposed/thrown away, rather than

taken orally, and this information will be recorded in the eCRF. Subjects will record time and day of administration in the subject's Diary.

6.5. Guidelines for Dose Modification

Reduction or interruption of the dose for toxicity may take place at any time according to the guidelines in [Table 6.3](#). Dose reduction/interruption guidelines for hematologic and non-hematologic treatment-related TEAEs are based on severity. Dose interruptions can be implemented at the discretion of the treating physician to manage intolerable or clinically significant toxicity. If a dose interruption is required, study assessments should be performed as scheduled, irrespective of the study treatment delay. Interruptions due to toxicity lasting >14 days require treatment discontinuation unless the Medical Monitor approves continuation.

The recommended dose reductions for AEs are provided in [Table 6.2](#).

Table 6.2: Recommended Dose Reductions for Pexidartinib for Adverse Reactions

Dose Reduction	New Total Daily Dose	Administration of Total Daily Dose
First	600 mg	200 mg in the morning and 400 mg in the evening
Second	400 mg	200 mg twice daily

Subjects unable to tolerate 200 mg orally twice daily will be discontinued. Once dose reduction takes place for toxicity, a dose re-escalation is not allowed.

The recommended dosage of pexidartinib for patients with mild to severe renal impairment (creatinine clearance [CrCL] 15 to 89 mL/min estimated by Cockcroft-Gault using actual body weight, [Section 10.3.1](#)) is 200 mg in the morning and 400 mg in the evening.

Dose-modification guidelines for treatment-emergent toxicities as well as guidelines for their management are presented in [Table 6.3](#). These parameters are only a guide and are not intended to supersede the clinical judgment of the treating physician. All adjustments should be communicated to the Sponsor's Medical Monitor or designee. Re-challenge with a reduced dose of pexidartinib may result in a recurrence of increased serum transaminases, bilirubin, or ALP. Investigators will ensure weekly liver monitoring tests for the first 8 weeks after re-challenge, then every 2 weeks for the next month, then every 3 months or more frequently as directed by the Investigator.

Additional information can be found in the *PL3397-A-U4003 Study Manual* and the *Pexidartinib IB*.

Table 6.3: Recommended Dosage Modifications for Pexidartinib for Adverse Reactions

Event	Severity	Pexidartinib Dosage Modifications
Hepatotoxicity		
Increased ALT and/or AST	>3 to 5 × ULN	
 Withhold and monitor liver tests weekly. If AST and ALT ≤3 × ULN within 4 weeks, resume at reduced dose. If AST or ALT not ≤3 × ULN in 4 weeks, permanently discontinue pexidartinib.

Event	Severity	Pexidartinib Dosage Modifications
	>5 to 10 × ULN	
 Withhold and monitor liver tests twice weekly. If AST and ALT $\leq 3 \times$ ULN within 4 weeks, resume at reduced dose. If AST or ALT not $\leq 3 \times$ ULN in 4 weeks, permanently discontinue pexidartinib.
	>10 × ULN	
 Permanently discontinue pexidartinib. Monitor liver tests twice weekly until AST or ALT $\leq 5 \times$ ULN, then weekly until $\leq 3 \times$ ULN.
Increased ALP ^a and GGT	ALP >2 × ULN with GGT >2 × ULN	
 Permanently discontinue pexidartinib. Monitor liver tests twice weekly until ALP ≤ 5 times ULN, then weekly until $\leq 2 \times$ ULN.
Increased bilirubin	TB >ULN to <2 × ULN or DB >ULN and <1.5 × ULN	
 Withhold and monitor liver tests twice weekly. If an alternate cause for increased bilirubin is confirmed and bilirubin <ULN within 4 weeks, resume at reduced dose. If bilirubin not <ULN in 4 weeks, permanently discontinue pexidartinib.
	TB $\geq 2 \times$ ULN or DB >1.5 × ULN	
 Permanently discontinue pexidartinib. Monitor liver tests twice weekly until bilirubin \leq ULN.
Adverse Reactions or Other Laboratory Abnormalities		
Any	Severe or intolerable	
 Withhold until improvement or resolution. Resume at a reduced dose upon improvement or resolution.

ALT = alanine aminotransferase; ALP = alkaline phosphatase; AST = aspartate aminotransferase; DB = direct bilirubin; GGT = gamma-glutamyl transferase; TB = total bilirubin; ULN = upper limit of normal.

^a Confirm ALP elevations as liver isozyme fraction.

Source: Pexidartinib Study Manual

Table 6.4: Additional Liver Evaluation

Evaluation*	Comments
Increase frequency of testing liver chemistries to twice per week, including INR and albumin, and continue until liver chemistries have stabilized, and then reduce to weekly until liver chemistries return to normal or baseline	Investigational treatment may be started after liver function tests recover to Grade 0 to 1 or baseline level, and in consultation with Medical Monitor
Detailed history focusing on medications and substances used: alcohol, change in medication dosages, new medications added, attention to use of acetaminophen, OTC medication use and recreational drug use. Check for change in diet or use of dietary supplements, with particular attention to dose and duration of any herbal product	Suspect medications will be discontinued or substituted for if possible
Detailed medical history and physical exam seeking new abnormalities	Evaluate abnormalities found

Evaluation*	Comments
Full serological evaluation for hepatitis A, B, C and E (IgG and IgM). Check for autoimmune hepatitis with serological laboratory studies	If viral hepatitis or autoimmune hepatitis suggested, have subject evaluated by hepatologist
Liver ultrasound performed to evaluate liver and biliary tree	Evaluate any abnormalities found
Check history for exposure to chemical agents	Remove chemical exposure and have subject seen by hepatologist
Obtain hepatology consult if liver function continues to rise beyond 14 days	Contact Medical Monitor

Ig = immunoglobulin; INR = international normalized ratio; OTC = over-the-counter.

*Cases are to be discussed with the Medical Monitor whenever investigational product is being held for liver function test abnormality.

All dose modifications (interruption, delay, reduction, and/or discontinuation) should be based on the worst preceding toxicity (National Cancer Institute-Common Terminology Criteria for Adverse Events [NCI-CTCAE] version 5.0) as shown in [Table 6.3](#). Dose increases are not permitted for pexidartinib. Dose modification decisions may be based on laboratory results.

Once the dose of pexidartinib has been reduced because of toxicity, all subsequent cycles should be administered at that lower dose level unless further dose reduction is required. More than 2 dose reductions are not allowed and if toxicity continues after 2 dose reductions, the subject will be withdrawn from the study treatment if further toxicity meeting the requirement for dose reduction occurs.

For Grade 3 or Grade 4 events, monitoring (including local laboratory tests when appropriate) should be performed frequently and at an interval no greater than 7 days until the AE is determined to be resolving.

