8.4.1.2. Adverse Events of Special Interest

Pexidartinib can cause serious and potentially fatal liver injury. Hepatotoxicity with ductopenia and cholestasis occurred in patients treated with pexidartinib. Across 768 patients who received pexidartinib in clinical trials, there were 2 irreversible cases of cholestatic liver injury. One patient died with advanced cancer and ongoing liver toxicity and 1 patient required a liver transplant. The mechanism of cholestatic hepatotoxicity is unknown and its occurrence cannot be predicted.

It is unknown whether liver injury occurs in the absence of increased transaminases. Avoid pexidartinib in patients with pre-existing increased serum transaminases; total bilirubin or direct bilirubin (>ULN); or active liver or biliary tract disease, including increased ALP. Taking pexidartinib with food increases drug exposure by 100% and may increase the risk of hepatotoxicity. Administer pexidartinib on an empty stomach, at least 1 hour before or 2 hours after a meal or snack. Monitor liver tests, including AST, ALT, total bilirubin, direct bilirubin, ALP and GGT, prior to initiation of pexidartinib, and as defined within the appropriate SoE for the cohorts (Section 1.3). Withhold and dose reduce, or permanently discontinue pexidartinib based on the severity of the hepatotoxicity (Table 6.3).

Combined Elevations of Aminotransferases and Bilirubin

Hepatic events (both serious and non-serious) which meet the potential Hy's Law criteria defined as an elevated (ALT and/or AST) $\geq 3 \times$ ULN and an elevated TBIL $> 2 \times$ ULN, regardless if it is due to disease progression per Investigator assessment, that may occur at different time points during the study conduct, should always be reported to the Sponsor. These events must be reported either by a SAVER form or eCRF, with the Investigator's assessment of seriousness, severity, causality, and a detailed narrative. These events should be reported within 24 hours of Investigator's awareness of the event regardless of seriousness. A targeted questionnaire will be available as an eCRF to collect relevant additional information for these potential cases.

If the subject discontinues study drug due to liver enzyme abnormalities, the subject will have additional clinical and laboratory evaluations as described in Section 10.2 in order to determine the nature and severity of the potential liver injury.

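### Table 6.4's restart comment is not tied to Table 6.3: read alone, it permits restarts after liver toxicity that Table 6.3 rules out, and the two tables need reconciling

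*Combined protocol and SAP*

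**What the plan says.** Section 6.5 handles liver toxicity in two adjacent tables.

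**Table 6.3** sets the action by analyte and severity.
- ALT/AST >3 to 10 × ULN: withhold, then "If AST and ALT ≤3 × ULN within 4 weeks, resume at reduced dose". If that level is not reached in 4 weeks, stop permanently.
- Lower bilirubin band (total >ULN to <2 × ULN, or direct >ULN and <1.5 × ULN): withhold, then "If an alternate cause for increased bilirubin is confirmed and bilirubin <ULN within 4 weeks, resume at reduced dose". If bilirubin is not below ULN in 4 weeks, stop permanently.
- ALT/AST >10 × ULN, ALP and GGT both >2 × ULN, and total bilirubin ≥2 × ULN or direct bilirubin >1.5 × ULN: stop permanently, with no route back.

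**Table 6.4** lists additional liver evaluations. Its first row says "Increase frequency of testing liver chemistries to twice per week, including INR and albumin". The comment beside it says "Investigational treatment may be started after liver function tests recover to Grade 0 to 1 or baseline level", "and in consultation with Medical Monitor". The footnote asks for discussion with the Medical Monitor "whenever investigational product is being held for liver function test abnormality".

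**Section 8.4.1.2** says that a subject who discontinues because of liver enzyme abnormalities will have "additional clinical and laboratory evaluations as described in Section 10.2".

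**The concern.** Hepatotoxicity is the drug's main stated risk. Section 2.3 says it may be fatal and that the cholestatic form may recur on re-challenge; Section 8.4.1.2 makes liver injury the adverse event of special interest. The rule for going back on drug after a liver event should therefore have one reading.

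It has two, because the Table 6.4 comment omits every limit that Table 6.3 imposes. A site or Medical Monitor working from one table could reach a different decision from one working from the other. Re-exposure and the Section 9.5.2 counts of events leading to discontinuation would then depend partly on which table was read. The laboratory summaries in that section use maximum and worst post-treatment values, which also depend on how often liver tests are drawn. The primary endpoint is not directly affected, since liver holds arise while a subject is on drug.

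The Section 8.4.1.2 reference adds a practical problem. Section 10.2 contains only the routine laboratory panel. The added work-up (serology, ultrasound, hepatology referral) is in Table 6.4, which no section text cites.

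**Working it through.** The plan gives no figure to reproduce, so the check applies both tables to the same liver values.

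**Inputs.** The Table 6.3 and Table 6.4 rules are as set out above. Section 10.5.3 names CTCAE version 5.0 for grading but gives no numeric liver cut-offs. The upper limit of Grade 1, *g* (in multiples of ULN), is therefore an assumption: 1.5 to 5 for ALT/AST and 1.05 to 2 for total bilirubin. Values below ULN are taken as Grade 0, baseline as normal, and ALT and AST as equal unless stated.

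**Rules compared.** Table 6.3: the action depends on the peak, the current value, weeks since the hold and, for bilirubin, a confirmed alternate cause. Table 6.4 read alone: restart is permitted, with consultation, if the current value ≤ *g* × ULN.

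| Case (× ULN) | Table 6.3 | Table 6.4 alone | Depends on *g*? |
|---|---|---|---|
| ALT/AST peak 12, later 0.9 | permanent stop | permitted | no |
| Total bilirubin peak 3, later 0.9 | permanent stop | permitted | no |
| ALP and GGT both >2, later normal | permanent stop | permitted | no |
| ALT/AST peak 8, 3.5 at week 4, later 0.9 | permanent stop at week 4 | permitted once at 0.9 | no |
| Total bilirubin peak 1.8, 0.9 at week 3, no alternate cause | no provision to resume; no stop ordered | permitted | no |
| Total bilirubin peak 1.8, 1.2 at week 4 | permanent stop | permitted at *g* = 1.25, 1.5, 2; not at 1.05 | yes |
| ALT/AST peak 4, 2.9 at week 3 | resume, reduced dose | not yet at *g* = 1.5, 2, 2.5; permitted at 3 and above | yes |
| ALT/AST peak 4, 3.5 at week 4 | permanent stop | permitted at *g* = 4, 5; not at 3 or below | yes |

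The first five rows diverge whatever the Grade 1 limit. The sixth diverges for some value above ULN whenever *g* > 1: the band runs from ULN to *g* × ULN. The last two show that, for ALT/AST peaks of >3 to 10 × ULN recovering within 4 weeks, the direction changes with *g*. At *g* = 3 the recovery levels coincide; below 3, Table 6.4 asks for more; above 3, Table 6.3 does. Table 6.3's time limit and dose reduction remain extra conditions throughout.

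**Testing frequency, ALT/AST >3 to 5 × ULN.** Table 6.3: 4 weeks × 1 = 4 panels. Table 6.4: 4 weeks × 2 = 8 panels if twice-weekly testing lasts the whole hold; fewer if values stabilise earlier, since it then drops to weekly.

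**Step-down wording.** The >10 × ULN row says "Monitor liver tests twice weekly until AST or ALT" is ≤5 × ULN, then weekly. With ALT 12 and AST 4 × ULN, AST already satisfies the condition, so the twice-weekly phase ends as soon as it starts. The resume rows require both enzymes to meet their limit.

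**Cross-reference.** Section 8.4.1.2 points to Section 10.2. Table 10.1 there covers chemistry, hematology, coagulation, urinalysis and hormone tests, with no liver work-up.

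**The case against.** The strongest reply is that the protocol already supplies a hierarchy. The text directly after Table 6.4 bases all dose modifications, discontinuation included, on the most severe earlier toxicity under Table 6.3. On that reading a peak of 12 × ULN stays in the permanent-stop row after recovery. Table 6.4 concerns evaluation, and its footnote speaks of drug being held, which a permanently stopped drug is not. The restart comment is a permission that needs Medical Monitor consultation; Section 2.3 likewise bars re-challenge without prior discussion with the Medical Monitor. Section 6.5 also ends treatment after toxicity interruptions longer than 14 days unless the Medical Monitor approves.

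Much of this stands, and it makes Table 6.3 the more natural governing table. It does not close the gap:
- Table 6.4 nowhere says that it yields, and Section 6.5 describes the Table 6.3 parameters as guidance that does not override clinical judgment.
- Consultation adds a reviewer without saying which criterion that reviewer applies.
- The footnote says when to call the Medical Monitor; it does not limit the restart comment. If Section 8.4.1.2 is meant to reach Table 6.4, as the content suggests, that table also covers subjects who have discontinued.

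A reader might infer three stronger things that the documents do not support. One is that the tables give opposite orders; Table 6.4 gives a conditional permission. Another is that Table 6.3 has the stricter ALT/AST recovery level throughout; without CTCAE cut-offs this cannot be shown. The third is that Table 6.3 orders a permanent stop when bilirubin is below ULN but no alternate cause is confirmed; it is silent on that case.

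It is also fair to say that the step-down and cross-reference points are not restart conflicts. They are separate wording errors in the same safety instructions.

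**Conclusion.** The inconsistency is real and limited. Independently of any grade cut-off, Table 6.4 read alone permits a restart that Table 6.3 excludes in three permanent-discontinuation rows and after failure to recover within 4 weeks, and one that Table 6.3 does not provide for when bilirubin has normalised without a confirmed alternate cause. If Grade 1 extends above ULN, which the documents do not state, the same holds for bilirubin still above ULN. An abnormal baseline could widen the gap, although Section 8.4.1.2 advises against use with pre-existing liver test elevations. No stricter ALT/AST recovery level in Table 6.3 is claimed.

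The testing-frequency, *or*/*and* and cross-reference inconsistencies each stand on the text. The number of subjects affected is unknown because the documents give no rates for these liver bands. The study is descriptive, so no test or power is at stake. The case for acting is that this is the drug's principal safety rule, in a study whose purpose includes re-treatment.

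**What to change.** Four changes of wording, with the clinical content left to the sponsor:
1. Reconcile Tables 6.3 and 6.4 and state which governs restart. Say explicitly whether the Table 6.4 comment applies to any row that Table 6.3 marks for permanent discontinuation, and whether Table 6.3's 4-week limits, reduced dose and alternate-cause condition apply to it.
2. Reconcile the testing frequency for ALT/AST >3 to 5 × ULN.
3. Reconcile the either-enzyme wording of the >10 × ULN step-down with the both-enzymes wording of the resume rows.
4. Point Section 8.4.1.2 to Table 6.4 instead of Section 10.2. Make this change together with the first, because it brings discontinued subjects expressly under the table that carries the restart comment.

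The cost is a protocol text amendment. No additional subjects are needed, and no procedure beyond those the tables already describe.
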